11.4.2.3 Multiplicity considerations

In order to handle the key secondary efficacy endpoint in addition to the primary efficacy endpoint, the overall type-I error will be controlled by the use of a sequential inferential approach. Statistical significance of the primary efficacy endpoint at the 0.05 alpha level is required before drawing inferential conclusions about the key secondary efficacy endpoint. This fixed hierarchical approach will ensure a strong control of the overall type-I error rate at the 0.05 level.

No further adjustments will be made for other secondary endpoints other than key secondary endpoints for which p-values will be provided for exploratory purpose only (no claim).

11.4.3 Analyses of safety data

The summary of safety results will be presented by treatment arm. No formal inferential testing will be performed. Summaries will be descriptive in nature.

Observation period

The observation period of safety data will be as follows:

- **Pre-treatment period** is defined as the time from the signed informed consent date up to the day of randomization.
- **TEAE period** is defined as the time from the day of randomization up to the last administration + 14 days (+ 7 days), or end of study, whichever comes first.
- **Post-treatment period** is defined as the time starting the day after the end of the TEAE period up to the end of the study (see definition in [Section 6.2.1](#)).
- **On-study observation period** is defined as the time from the day of randomization up to the end of the study (see definition in [Section 6.2.1](#)).

All safety analyses will be performed on the safety population using the following common rules:

- The potentially clinically significant abnormality (PCSA) values are defined as abnormal values considered medically important by the Sponsor according to predefined

criteria/thresholds based on literature review and defined by the Sponsor for clinical laboratory tests and vital signs.

- PCSA criteria will be determined which patients had at least 1 PCSA during the TEAE period, taking into account all evaluations performed during the TEAE period, including unscheduled or repeated evaluations. The number of all such patients will be the numerator for the PCSA percentage.

Drug-induced liver injury

The liver function tests, namely ALT, AST, alkaline phosphatase, and total bilirubin, are used to assess possible drug-induced liver toxicity. The proportion of patients with PCSA values at any post-baseline visit by baseline status will be displayed by treatment arm for each parameter.

A graph of distribution of peak values of ALT versus peak values of total bilirubin will also be presented. Note that the ALT and total bilirubin values are presented on a logarithmic scale. The graph will be divided into 4 quadrants with a vertical line corresponding to $3 \times \text{ULN}$ for ALT and a horizontal line corresponding to $2 \times \text{ULN}$ for total bilirubin.

The incidence of liver-related AEs will be summarized by treatment arm. The selection of preferred terms will be based on standardized MedDRA query (SMQ) "Hepatic disorder."

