10.1.1.1 Study site visit

10.1.1.1 Randomization visit (Visit 1 / Week 0 / D1)

Blood sampling should be completed before IMP administration.

This visit includes:

- On-site visit.
- Complete and collect written informed consent for the study by the randomization visit. Patient number will be allocated by the registration center. The patient number is composed of a 9-digit number containing the 3-digit country code, the 3-digit center code, and the 3-digit patient chronological number (3-digit patient chronological number is 001 for the first patient screened in a center, 002 for the second patient screened in the same center).

Note: The written informed consent can be obtained any time between ACS diagnosis and the randomization visit (see [Section 1.2](#)).

- Confirm inclusion and exclusion criteria.
- Collect information about therapeutic intervention such as ACS culprit vessels, IVUS imaging locations (refer to [Section 17](#), Appendix D for vessel locations), and types of stent placed at the PCI (BMS or DES).

- Contact the registration center to notify the patient enrollment. After the final confirmation of inclusion and exclusion criteria at the registration center, the arm to which the patient randomized to is communicated.
- Demographics (age, gender, race, ethnicity).
- Collect contact information (address, email, home and cell phone numbers) of the patient, patient's family members, and patient's primary care physician / cardiologist.
- Patient's medical and surgical history (including menopausal status, and family history), alcohol habits, smoking habits, lipid parameters including LDL-C used for the study eligibility, and HbA1c.
- Collect patient's history of CV disease.
- Record use of LMT including statins and prescription or over-the-counter non-statin LMTs within 1 month prior to Visit 1.
- Record of all concomitant medications including CV medications.
- Collection of adverse events including CV events (if any).
- Collection of results of hepatitis B virus surface antigen and antibody tested at the time of ACS diagnosis and PCI.

Note: If the hepatitis B virus surface antigen and antibody titers are not checked, they must be measured prior to the randomization visit and the results must be recorded at the randomization visit (see [Section 7.1](#)).

- Physical examination including vital signs: heart rate and sitting SBP and DBP.
- Body weight and height.
- EQ-5D patient questionnaire.

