11.4.3.2 Laboratory data and vital signs

See also [Section 9.2.2](#) and [Section 9.2.3](#).

The descriptive statistics (including mean, median, Q1, Q3, SE, minimum and maximum) of all laboratory variables and all vital signs parameters (raw data and changes from baseline) will be calculated for each time point, last and worst values assessed during the treatment period and presented by treatment arm. For selected parameters, mean changes from baseline with the corresponding SE will be plotted over time (at same time points) in each treatment arm. The incidence of PCSAs at any time during the TEAE period (on-treatment PCSAs) will be summarized by treatment arm regardless of the baseline level and/or according to the following baseline categories:

- Normal / missing.
- Abnormal according to PCSA criterion or criteria.

For laboratory parameters for which PCSA criterion are not defined, similar table(s) using the normal range could be provided.

Hepatitis C virus test:

The number and percentage of patients with an observed seroconversion of Hepatitis C virus test will be provided by treatment arm.

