11.4.4 Analyses of other endpoints

All analyses for other endpoints will be performed on the safety population. The baseline value is defined as the last available value before randomization.

The number and percentage of patients with 2 consecutive calculated LDL-C <25 mg/dL and calculated LDL-C <15 mg/dL, respectively, will be provided by treatment arm. The time interval between 2 consecutive calculated LDL-C should be spaced out by at least 21 days.

Exploratory variables defined in [Section 9.3](#) will be summarized by time points for each treatment arm. For hs-CRP, the incidence of PCSA at any time during the TEAE period will be also summarized by treatment arm using descriptive statistics.

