##### ***Observation period***

The observation period of safety data will be as follows:

- **Pre-treatment** period is defined as the time from the signed informed consent date up to the day of randomization.
- **Treatment-emergent adverse event (TEAE)** period is defined as the time from the day of randomization to the last study treatment administration + 21 days, or end of study, whichever comes first in both the alirocumab and SoC groups.

- **Post-treatment** period is defined as the time starting the day after the end of the TEAE period up to the end of the study.
- **On-study observation** period is defined as the time from the day of randomization until the end of the study.

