##### ***General common rules***

All safety analyses will be performed on the safety population as defined in [Section 2.3.2](#), unless otherwise specified, using the following common rules:

- Safety data in patients who do not belong to the safety population (eg, exposed but not randomized) will be listed separately;
- The baseline value is defined as the last available value before randomization, unless otherwise specified;
- The potentially clinically significant abnormality (PCSA) values are defined as abnormal values considered medically important by the Sponsor according to predefined criteria/thresholds based on literature review and defined by the Sponsor for clinical laboratory tests, vital signs (PCSA defined in the document “Analysis and reporting safety data from clinical trials through the Clinical Study Report (CSR) (Version Number: 3.0)” [\[Appendix A\]](#))
- PCSA criteria will determine which patients had at least 1 PCSA during the TEAE period, taking into account all evaluations performed during the TEAE period, including nonscheduled or repeated evaluations.
- The treatment-emergent PCSA denominator by group for a given parameter will be based on the number of patients assessed for that given parameter in the TEAE period by treatment group on the safety population.
- All measurements, scheduled or unscheduled, fasting or not fasting, will be assigned to analysis windows defined in [Section 2.5.4.2, Table 4](#).
- For quantitative safety parameters, descriptive statistics will be used to summarize results and change from baseline values by visit and treatment group using analysis windows defined in [Section 2.5.4.2, Table 4](#). Summaries will include the last on-treatment value and the worst on-treatment value. The worst value is defined as the nadir and/or the peak value during the treatment period according to the direction (minimum or maximum) of the abnormality as defined in the PCSA list.

Analyses performed according to diabetic status will be done using the CMQ definition (regardless of the ongoing status) ([Section 2.1.1](#)).

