#### ***2.4.5.4 Analyses of vital sign variables***

The summary statistics (including number, mean, median, Q1, Q3, standard deviation, minimum, and maximum) of all vital sign variables (values and changes from baseline) will be calculated for each visit or study assessment (baseline, each post-baseline time point, last on-treatment and worst on-treatment value) by treatment group during the treatment period. In addition, for some parameters of interest, mean changes from baseline with the corresponding standard error could be plotted over time in each treatment group.

Vital signs without position filled in will only be used for the PCSA analysis described below.

The incidence of PCSAs at any time during the TEAE period will be summarized by treatment group.

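### The general PCSA rule, read as written, counts pre-dose Day 1 baseline values as on-treatment abnormalities

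*Protocol*

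**What the plan says.** **Period.** In SAP 2.1.4 the TEAE "period is defined as the time from the day of randomization to the last study treatment administration + 21 days, or end of study", whichever is earlier, in both arms. Protocol 11.4.3 uses the same start and the same 21 days, written as 14 plus 7. Both documents also let the pre-treatment period run up to the day of randomization.

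**Counting rule.** Under protocol 11.4.3 a patient has a PCSA "taking into account all evaluations performed during the TEAE period, including unscheduled or repeated evaluations". SAP 2.4.5 (General common rules) repeats this: "taking into account all evaluations performed during the TEAE period, including nonscheduled or repeated evaluations". The SAP denominator is the number of patients assessed for the parameter in the TEAE period.

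**Visit 1.** Visit 1 is Day 1. Protocol 10.1.1.1 says of this visit: "Blood sampling should be completed before IMP administration". Vital signs are also taken then, and the first injection follows once all planned assessments are done. SAP 2.4.5 defines baseline as the last value available before randomization.

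**Tables.**
- Protocol 11.4.3.2: "The incidence of PCSAs at any time during the TEAE period (on-treatment PCSAs) will be summarized by treatment arm regardless of the baseline level", and/or by baseline category (normal or missing, versus abnormal by PCSA criterion). SAP 2.4.5.3 keeps the and/or for laboratory data.
- Vital signs, SAP 2.4.5.4: "The incidence of PCSAs at any time during the TEAE period will be summarized by treatment group". No baseline split is stated there.
- hs-CRP, protocol 11.4.4: "For hs-CRP, the incidence of PCSA at any time during the TEAE period will be also summarized by treatment arm". SAP 2.4.6.1 (hs-CRP) and 2.4.6.2 (HbA1c) state no split of PCSAs by baseline PCSA status.
- Liver tests (protocol 11.4.3 and SAP 2.4.5.3): limited to post-baseline visits and shown by baseline status.

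**The concern.** The same Day 1 value is baseline under one definition and on-treatment under another, and the PCSA rule contains nothing to separate the two. A patient abnormal only before treatment enters the numerator of a table that the protocol labels on-treatment. A patient with no later value still enters the denominator. Where the baseline split is produced, a patient whose Day 1 value is abnormal already qualifies, so the abnormal-at-baseline row tends to 100% and carries no information.

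Two programmers could produce different safety tables from this text. If the literal reading is programmed, the percentages do not describe what happened on treatment and the ratio between arms is pulled toward 1. Baseline abnormality is plausible in patients randomized within 4 weeks of an acute coronary syndrome.

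A related looseness is that an adverse event starting on Day 1 before the injection fits both the pre-treatment and the TEAE definitions.

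**Working it through.** The documents state no PCSA rate, so there is no planned figure to reproduce. The PCSA thresholds are not in the available text either. The rates below are assumptions.

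**1. Does the text count Day 1?** The TEAE period opens on the randomization date, Visit 1 is that date, and all evaluations in the period count. No sentence in the general rule removes baseline or pre-dose values. Followed literally, Day 1 counts.

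**2. Formulas, per arm, among patients with later values.** Let b be the proportion with a PCSA at baseline (equal in the arms by randomization), p the incidence of a new PCSA in patients without one at baseline, and r the proportion of baseline PCSAs that recur at a later evaluation.

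- Literal rule: b + (1 − b)p
- Post-baseline values only: br + (1 − b)p
- Excess under the literal rule: b(1 − r)

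The proper comparator is the second line, not p alone, because a corrected all-patients table still contains baseline abnormalities that persist.

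**3. Numbers, assuming p = 5% versus 10% and equal r in both arms.** Example for b = 10%:

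- Literal: 0.10 + 0.90 × 0.05 = 14.5%; 0.10 + 0.90 × 0.10 = 19.0%; ratio 1.31
- Corrected, r = 50%: 0.05 + 0.045 = 9.5%; 0.05 + 0.09 = 14.0%; ratio 1.47
- Corrected, r = 90%: 0.09 + 0.045 = 13.5%; 0.09 + 0.09 = 18.0%; ratio 1.33

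| b | Literal | Corrected, r = 50% | Corrected, r = 90% | Difference in all three (points) |
|---|---|---|---|---|
| 5% | 9.75% v 14.5% (1.49) | 7.25% v 12.0% (1.66) | 9.25% v 14.0% (1.51) | 4.75 |
| 10% | 14.5% v 19.0% (1.31) | 9.5% v 14.0% (1.47) | 13.5% v 18.0% (1.33) | 4.5 |
| 20% | 24.0% v 28.0% (1.17) | 14.0% v 18.0% (1.29) | 22.0% v 26.0% (1.18) | 4.0 |
| 30% | 33.5% v 37.0% (1.10) | 18.5% v 22.0% (1.19) | 30.5% v 34.0% (1.11) | 3.5 |

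**4. Absolute difference.** With equal r, the excess b(1 − r) is the same in both arms and cancels: the difference is (1 − b)(p1 − p0) either way. If r differs by arm, the literal rule drops b(r1 − r0) from the difference. In the extreme case where a baseline PCSA says nothing about later values (r = p in each arm), the corrected table shows 5% v 10% (5.0 points, ratio 2.0) against 4.5 points and 1.31 at b = 10%.

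**5. Rows not affected.** Where the Day 1 value is the baseline value, a patient with a Day 1 PCSA is not in the normal-at-baseline row, which shows p under either reading. The liver tables already exclude baseline.

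**6. Denominator.** Patients with only a Day 1 value are added to the SAP denominator. They can move the percentage either way, so the formulas above leave them out.

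**7. hs-CRP timing.** It is sampled only at Weeks 0 and 36. A last injection on Day 239 closes the TEAE period on Day 260. The Week 36 visit is Day 253 ± 14, so up to Day 267. With that last dose, only a Week 36 sample on Days 261 to 267 would leave the pre-dose value as the sole one counted.

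**The case against.** The strongest reply is that the authors plainly meant post-baseline values. Baseline is defined separately. The counts are called treatment-emergent or on-treatment. SAP 2.4.5.3 and 2.4.5.4 list baseline apart from on-treatment values, the first window in SAP Table 4 opens on study day 15, and a row that can only show 100% is not a plausible plan. This is good evidence of intent, but none of it limits the PCSA count. The Table 4 windows cannot be the filter: they leave gaps (for example Days 43 to 77), whereas the PCSA rule takes every evaluation, including unscheduled ones. The authors wrote the post-baseline limit for liver tests and did not write it in the general rule.

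Several counter-arguments do stand. Some PCSA criteria include a change from baseline, which a baseline value cannot meet against itself, although SAP 2.5.3 falls back to the threshold alone when that condition is missing. The protocol's optional split covers vital signs. Late hs-CRP samples are the exception: Day 260 falls after the Day 253 target, early discontinuers have an end-of-treatment assessment, and hs-CRP is exploratory. For adverse events with incomplete onset, the SAP already defaults to treatment-emergent, so only a fully timed pre-injection event stays ambiguous.

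A reader might infer that the rule hides a real safety difference, or that the fall from 2.0 to 1.31 measures the damage. The documents do not support either inference. Much of that fall comes from pooling patients already abnormal at baseline, which a date filter does not undo, and with equal persistence the absolute difference does not move.

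**Conclusion.** The point holds as a minor one. The general PCSA rule, followed as written, includes pre-dose Day 1 values and gives a table that does not match its label. It inflates the all-patients percentages, admits patients without follow-up values to the denominator, empties the abnormal-at-baseline row of meaning, and moves the ratio toward 1.

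Under the assumed 5% versus 10% new incidence and 10% baseline prevalence, the inflation is 5 points per arm at 50% persistence and 1 point at 90%. The corresponding ratio falls from 1.47 or 1.33 to 1.31. These sizes rest entirely on assumed prevalence, incidence and persistence. Concealment of a difference is not shown: safety is summarized without formal testing, and the normal-at-baseline row and the liver tables are sound. The and/or wording does not, however, guarantee that the normal-at-baseline row will be produced.

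**What to change.** In protocol 11.4.3 and SAP 2.1.4 and 2.4.5:

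- State that PCSA numerators and denominators, and the last and worst on-treatment values, use only post-baseline evaluations, defined as study day 2 onward in both arms. A rule tied to the time of the first injection would have no counterpart in the standard-of-care arm.
- Treat Visit 1 values as baseline only.
- Assign Day 1 to a single period so that the pre-treatment and TEAE periods do not overlap. If Day 1 stays in the TEAE period for adverse events, the PCSA rule still needs its own start at day 2.
- Replace the and/or with a required split by baseline status for all PCSA tables, including vital signs, hs-CRP and HbA1c.

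The cost is a sentence or two, a date filter in the programs and the added baseline-status rows. No new data are needed. PCSA counts and denominators become slightly smaller.

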11.4.3.1 Adverse events

The adverse events are defined as follows:

- Pre-treatment AEs are AEs that develop, worsen, or become serious during the pre-treatment period
- TEAEs are AEs that develop, worsen, or become serious during the TEAE period
- Post-treatment AEs are AEs that develop, worsen, or become serious during the post-treatment period

AE incidence tables will be presented by SOC (sorted by internationally agreed order), HLT, HLT, and PT sorted in alphabetical order for each treatment arm, and the number (n) and percentage (%) of patients experiencing an AE. Multiple occurrences of the same event in the same patient will be counted only once in the tables within a treatment phase. The denominator for computation of percentages is the safety population within each treatment group.

AE incidence table will be provided by treatment arm for all types of TEAEs: all TEAEs, all treatment emergent AESI (defined with a PT or a prespecified grouping), all treatment emerged SAEs, and all TEAEs leading to permanent treatment discontinuation.

Deaths

The following deaths summaries will be generated:

- Number (%) of patients who die during study period (TEAE, on-study, post-study) summarized on the safety population by treatment received

- Death in non-randomized patients or randomized and not treated patients
- TEAE leading to death (death as an outcome on the AE CRF page as reported by the Investigator/sub-Investigator) by primary SOC, HLGT, HLT, and PT showing number (%) of patients sorted by internationally agreed order of SOC and alphabetic order of HLGT, HLT, and PT.

Adjudicated CV events

The number and percentage of patients experiencing a positively adjudicated CV event will be presented by treatment arm overall and by category of adjudication.

11.4.3.2 Laboratory data and vital signs

See also [Section 9.2.2](#) and [Section 9.2.3](#).

The descriptive statistics (including mean, median, Q1, Q3, SE, minimum and maximum) of all laboratory variables and all vital signs parameters (raw data and changes from baseline) will be calculated for each time point, last and worst values assessed during the treatment period and presented by treatment arm. For selected parameters, mean changes from baseline with the corresponding SE will be plotted over time (at same time points) in each treatment arm. The incidence of PCSAs at any time during the TEAE period (on-treatment PCSAs) will be summarized by treatment arm regardless of the baseline level and/or according to the following baseline categories:

- Normal / missing.
- Abnormal according to PCSA criterion or criteria.

For laboratory parameters for which PCSA criterion are not defined, similar table(s) using the normal range could be provided.

Hepatitis C virus test:

The number and percentage of patients with an observed seroconversion of Hepatitis C virus test will be provided by treatment arm.

11.4.4 Analyses of other endpoints

All analyses for other endpoints will be performed on the safety population. The baseline value is defined as the last available value before randomization.

The number and percentage of patients with 2 consecutive calculated LDL-C <25 mg/dL and calculated LDL-C <15 mg/dL, respectively, will be provided by treatment arm. The time interval between 2 consecutive calculated LDL-C should be spaced out by at least 21 days.

Exploratory variables defined in [Section 9.3](#) will be summarized by time points for each treatment arm. For hs-CRP, the incidence of PCSA at any time during the TEAE period will be also summarized by treatment arm using descriptive statistics.

